5.1.8. Examination of Subgroups

Subgroup analyses will be conducted for primary endpoint on the Full Analysis Set. It should be noted that the study is not designed to detect treatment differences within subgroups.

The following subgroups may be assessed and described within the exploratory analysis sections; however, categories for sub-grouping will be confirmed further based on the empirical data:

- Gender:
 - Female
 - Male
- Age (years):
 - 40 to 49
 - 50 to 59
 - ≥ 60
- Race in all categories:
 - American Indian or Alaska Native
 - Asian
 - Black or African American
 - Native Hawaiian or Other Pacific Islander
 - White
 - Other
- Body Mass Index
 - Underweight: 15 to 18.4
 - Normal: 18.5 to 25
 - Overweight: 26 to 30
 - Moderately Obese: 31 to 35
 - Severely Obese: 36 to 40
- Severity at baseline
 - NRS Score
 - Moderate 5 to 6
 - Severe ≥ 7
 - WOMAC Pain
 - 0 to 9
 - 10 to 20
- Disease Symptoms
 - < 6 months

- 6 months to 1 year
 - 2 to 5 years
 - > 5 years
- Pain in the target knee
 - 30 days to 59 days
 - 2 months to 1 year
 - 2 to 5 years
 - > 5 years
- Washout Period
 - Less than 7 days
 - 7 days
 - 7 to 14 days
- NSAIDs at Screening
 - Type of NSAIDs
 - Prescribed
 - Physician's recommended OTC
 - Number of NSAIDs
 - <=5
 - > 5
 - Prescription
 - At least 3 days per week for last 30 days
 - More than 3 days per week for the last 30 days
 - At least 3 days per week for more than 30 days
 - More than 3 days per week for more than 30 days
 - OTC
 - At least 3 days per week for last 30 days
 - More than 3 days per week for the last 30 days
 - At least 3 days per week for more than 30 days
 - More than 3 days per week for more than 30 days
- eDiary compliance at Screening
 - 70%
 - > 70%
- Rescue Medication during Screening
 - <= 4 tablets
 - > 4 tablets
 - None
- Used rescue medication within 2 calendar days prior to Baseline Visit
- Other concomitant Medications (Excluding Pain Medications)
 - Corticosteroids
 - ACE inhibitors
 - Diuretics

- Methotrexate
- Cyclosporine
- Others
- Minor Surgeries
 - Type of surgery
 - Number of years prior to screening

6. Study Patients/Subjects and Demographics

6.1. Disposition of Patients/Subjects and Withdrawals

Disposition will include tabulations by treatment group and overall of the number of subjects randomized into each treatment group, the number of subjects who received treatment, tabulated reasons for discontinuation from the study, and number of subjects in each analysis population.

A by-subject listing of all disposition information will be presented.

6.2. Protocol Violations and Deviations

A by-subject listing of all protocol deviations and violations will be presented in Clinical Study Report from the source data.

6.3. Demographics and Other Baseline Characteristics

Descriptive summaries of demographic (age, gender, race, ethnicity, height, weight, and BMI) and other baseline characteristics (baseline NRS scores, baseline WOMAC scores, baseline PGA, and baseline severity as measured by categories of NRS: Moderate 5 to 6, Severe \geq 7, WOMAC Pain: 0 to 9, 10 to 20) will be provided for all patients by treatment group and overall. These tabulations will be repeated for SAF populations. All demographic and other baseline characteristics will be presented in subject listings.

6.4. Medical History

Subjects reporting various medical histories, grouped by MedDRA system organ class and preferred term will be listed.

6.5. Prior Medications

A prior medication is any non-protocol specified drug or substance administered prior to first date of study drug. Subjects taking prior medications will be listed by Anatomical Therapeutic Chemical (ATC) classification level 4 and preferred term and are coded using WHO-DD.

Statistical Analysis Plan,
Sponsor Noven Pharmaceuticals, Inc.
Protocol Number HP-5000-US-05
[REDACTED]

6.6. Concomitant Medications

Concomitant medications will be listed similarly to Prior medications. A concomitant medication is any non-protocol specified drug or substance administered during participation in the study on or after first date of study drug. A medication can be considered both concomitant and prior if the subject took medication prior to the study and continued taking it after first study drug administration.

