9.10.2 Prohibited Therapies

Any NSAIDs (selective or nonselective), any opioids, APAP (>2 g/day), ASA (>81 mg/day), corticosteroids (a stable dose by inhalation for seasonal allergies and/or topical use for dermatologic allergies are allowed), anticonvulsants (i.e., pregabalin and gabapentin etc...), muscle relaxants, other oral analgesics (prescription and/or OTC), antidepressants prescribed for the control of chronic pain syndromes, antihistamine with a sedative effect, sedatives for insomnia, topical products on the knee including methyl salicylate, camphor, menthol, methylsulfonylmethane, [REDACTED] or capsaicin, any intra-articular treatments for the knee, any nonpharmaceutical therapy or device to relieve knee pain (including physiotherapy, massage therapy, hot wax therapy etc.) are not allowed to be taken during the study.

Subjects will be allowed to continue stable ASA therapy not for OA pain (up to 81 mg/day).

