13.4.1.3 Demographics and Other Baseline Characteristics

These analyses will be conducted for all analysis populations. Demographic variables will include age, gender, height, and weight. Information on race and ethnicity will be collected for any eventual analysis of differences in response to study drug, in accordance with local regulatory requirements. Baseline subject characteristics will include medical history, physical examination findings, and previous OA treatment modalities.

Prior and concomitant medications will be summarized by treatment group, by the number and percentage of subjects taking each medication, classified using World Health Organization Drug Dictionary (WHO-DD) Anatomical Therapeutic Chemical (ATC) classes and preferred terms.

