13.4.4.2 Concomitant Medications

Prior and concomitant therapies will be summarized for the Safety population. All prior and concomitant medications recorded in the eCRF will be coded to generic term and all matching Anatomic Therapeutic Classification (ATC) codes using the current version (2017) of WHO Drug. Summaries will be prepared using the coded generic term. All prior and concomitant medications recorded in the eCRF will be listed.

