7.1. Primary Efficacy Analysis

The estimand in the primary analysis for efficacy for each dose is the difference between treatments groups (each HP-5000 treatment group vs. placebo) in the change from Baseline to Week 4 in WOMAC pain score in all subjects as randomized, under the assumption that all randomized patients remain on their randomized treatment throughout the trial.

AD-ST-33.04 Effective date: 30-Jun-2017

Version 1.0 | Date 21-Oct-2019 | AD-PR-109.01 Effective date: 26-Jun-2017

Page 24 of 124

Statistical Analysis Plan,
 Sponsor Noven Pharmaceuticals, Inc.
 Protocol Number HP-5000-US-05
 [REDACTED]

The comparisons of interest are:

- HP-5000 [REDACTED] versus placebo
- HP-5000 [REDACTED] versus placebo

WOMAC scores obtained 24 hours after removal/detachment of the study medication or WOMAC scores obtained within 24 the subject used rescue medication will be excluded as outliers. Outliers will be defined *a priori* as (i) WOMAC scores obtained more than 24 hours after removal/detachment of double-blind study medication; or (ii) WOMAC scores obtained within 24 hours the subject used rescue medication.

The change from Baseline to Week 4 in the WOMAC pain score will be analyzed using a mixed model repeated measures (MMRM) analysis. The MMRM model will include change from baseline in WOMAC pain score as the repeated dependent variable, with treatment (HP-5000-[REDACTED], HP-5000-[REDACTED], and placebo), visit, treatment-by-visit interaction, and the baseline WOMAC pain score as covariates. The mean difference of change will be compared for each active treatment arm, and overall active against placebo. An unstructured covariance matrix will be assumed. If the unstructured matrix fails to converge, a series of other covariance structures will be tested (AR(1), Toeplitz, and Compound Symmetry). The covariance structure which converges with the lowest Akaike information criterion (AIC) score will be chosen and noted in the resulting table. The Kenward-Roger approximation for denominator degrees of freedom will be implemented, and the restricted maximum likelihood (REML) approach for estimation will be specified in the model code.

Below is example SAS code for conducting the MMRM analysis specified. Note, the macro wrapper used in different covariance structures is not shown below (specified with type option):

[figure not shown]
[figure not shown]
[figure not shown]
```
ods output lsmeans = lsmn1
      lsmestimates = lsmest1

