8.6. Pharmacokinetic Analysis

Plasma concentrations of diclofenac (for both HP-5000 [REDACTED] and HP-5000-[REDACTED] will be summarized with descriptive statistics by treatment group.

A by-subject listing of all plasma concentration data will be presented.

9. Changes from Planned Analysis

None

10. Final Database Transfer

After finalization of the analysis, the following will be transferred to the study sponsor:

- Randomization List
- Statistical Analysis Plan
- Data Management Plan
- Annotated CRF
- All SAS code used in the project for statistical analysis, report tables generation, and analysis dataset creation (including all source code for any macros that may be used)
- Tables, listings, and figures as included in the clinical study report
- Final SAS datasets, with full audit trail from initial data entry through final accepted version
- ADaM datasets that are necessary for analysis will be programmed in addition to SDTM (to be modeled in accordance with the Analysis Data Model version 2.1: Implementation Guide version 1.0, and the CDISC Study Data Tabulation Model version 1.4: Implementation Guide version 3.2)
- Define.xml for ADaM and SDTM data sets (to be modeled in accordance with the CDISC Define-XML Specification Version 2.0)
- Study data and analysis data reviewer guides (to be modeled in accordance with the Analysis Data Reviewer's Guide Completion Guidelines Version 1.1, and the Study Data Reviewer's Guide Completion Guidelines Version 1.2) for any unavoidable CDISC checker errors or warnings (found using Pinnacle21)
- Pinnacle21 reports with explanation for errors/warnings if any
- Relevant Correspondence

Database archiving at Premier is performed in accordance with Premier SOPs, which ensure security, integrity, disaster recovery, and adequate backup.

11. References

1. Noven Pharmaceuticals, Inc. protocol number HP-5000-US-05, *A 4-week, Randomized, Double-blind, Multicenter, Placebo-controlled Phase 2 Study to Evaluate the Efficacy and*

AD-ST-33.04 Effective date: 30-Jun-2017

Statistical Analysis Plan,
Sponsor Noven Pharmaceuticals, Inc.
Protocol Number HP-5000-US-05
[REDACTED]

Safety of HP-5000 in Subjects with Osteoarthritis (OA) of the Knee, dated 12-JAN-2018,
Amendment 2

2. [REDACTED]

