14.1 Demographics and Baseline Tables		
14.1.1	All Enrolled Subjects	Study Populations and Subject Disposition
14.1.2	SAF	Demographics and Baseline Characteristics
14.1.3	ITT	Previous Osteoarthritis (OA) Treatment Modalities
14.1.4	ITT	Exposure to Study Drug
14.1.5	ITT	Previous NSAID Treatments

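### The SAP replaces the protocol's by-arm concomitant medication summary with a listing, without declaring it, and has no rule for WOMAC scores obtained on prohibited analgesics

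*SAP*

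**What the plan says.** **Concomitant medication.**
- Protocol 13.4.1.3: "Prior and concomitant medications will be summarized by treatment group, by the number and percentage of subjects taking each medication".
- Protocol 13.4.4.2: "Prior and concomitant therapies will be summarized for the Safety population".
- SAP 6.6: "Concomitant medications will be listed similarly to Prior medications". SAP 6.5 likewise only lists prior medications.
- SAP 13.1: the only medication tables are 14.1.3, on previous OA treatment, and 14.1.5, titled "Previous NSAID Treatments". Neither covers medication taken during the double-blind phase.
- SAP section 9, headed "9. Changes from Planned Analysis", has the single entry None.

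**Prohibited analgesics.**
- Protocol 9.10.2 bars, among others, "Any NSAIDs (selective or nonselective), any opioids, APAP (>2 g/day), ASA (>81 mg/day), corticosteroids", other oral analgesics and topical analgesic products on the knee.
- SAP 7.1 excludes two kinds of WOMAC score from the primary analysis. Rule (i) covers scores taken more than 24 hours after the patch came off. Rule (ii) is "or (ii) WOMAC scores obtained within 24 hours the subject used rescue medication".
- SAP 7.1.1 recognises two intercurrent events: discontinuation and rescue use.
- Neither section mentions prohibited medication.

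**Where prohibited use would still appear.** Listing 16.2.4.3 gives each medication by subject, with dates, under the treatment received. SAP 6.2 adds: "A by-subject listing of all protocol deviations and violations will be presented".

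**The concern.** Every subject must have been on stable NSAID therapy before screening (protocol 8.2.1, criteria 2c and 2d), is then washed out, and must show enough pain to be randomised (protocol 7.1). A subject without relief going back to an NSAID is a foreseeable event.

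The estimand in SAP 7.1 supposes that everyone remains on randomised treatment. A score obtained while another analgesic is acting does not measure the patch alone. As written, the plan would set aside a score because of permitted acetaminophen and retain one obtained on a prohibited NSAID or opioid.

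If subjects on placebo return to analgesics more often, the placebo arm looks better and the contrast shrinks. The by-arm table that the protocol asks for is the display that would show whether this happened, and the SAP omits it. The trial informs the choice of what advances to phase III (SAP section 2), at a stated power of only about 67%.

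**Working it through.** **1. Table against listing.** The protocol asks for number and percentage per medication by treatment group (13.4.1.3) and a summary for the Safety population (13.4.4.2). The SAP plans a listing, and the planned tables in SAP 13.1 contain no concomitant medication table. This is a departure from the protocol, so the entry None in section 9 is incorrect. No assumption is needed.

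**2. How an affected score reaches the primary model.** Take a Week 4 WOMAC score from a subject who is wearing the patch and taking an NSAID.
- Rule (i) does not apply, because the patch is on.
- Rule (ii) does not apply, because the NSAID is not rescue medication. Acetaminophen taken as rescue would fall under this rule.
- The FAS (SAP section 5) has no exclusion for deviations, and no per-protocol set is defined. The PK set does allow exclusion for violations that may affect PK.
- Withdrawal for non-compliance is optional (protocol 8.2.3).
- The concomitant medication subgroup in SAP 5.1.8 leaves out pain medications.

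The score is therefore used. This follows from silence, not from a stated decision.

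**3. Is the rescue rule settled?** In the 7.1.1 summary table, the primary analysis row shows NO for discontinuation and YES for rescue. If NO means that data after discontinuation are not used, which agrees with rule (i), then YES suggests that rescue-affected data are used, which conflicts with rule (ii). Rule (ii) is also absent from protocol 13.4.3.1 and not declared in section 9.

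**4. The plan's own figure.** The point does not depend on power, but 67% is the only relevant number given. The inputs are 75 per active arm and 150 on placebo (SAP 3.2) and two-sided 0.05 (SAP 4.1). The effect size is redacted in the current protocol and SAP; 0.32 is legible only in the synopsis of an earlier protocol version.
- SE in SD units = √(1/75 + 1/150) = √0.02 = 0.1414
- Power = Φ(0.32/0.1414 − 1.960) = Φ(0.303) = 61.9%

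A power of 67% would need an effect of about 0.34. Alternatively, 67% could be the chance of observing at least about 0.26 when the truth is 0.32. Because the current effect size and threshold are redacted, this check is inconclusive and does not show 67% to be wrong.

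**5. Illustrative size.** Let g be prohibited use at Week 4 on placebo minus active, and b the benefit of that use in SD. Then:
- diluted contrast = 0.32 − g × b
- power = Φ(contrast/0.1414 − 1.960)

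Both g and b are assumptions; the documents give neither.

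| g | b = 0.3 | b = 0.5 | b = 0.8 |
|---|---|---|---|
| 0 | 0.320 (61.9%) | 0.320 (61.9%) | 0.320 (61.9%) |
| 5% | 0.305 (57.8%) | 0.295 (55.0%) | 0.280 (50.8%) |
| 10% | 0.290 (53.6%) | 0.270 (48.0%) | 0.240 (39.6%) |
| 20% | 0.260 (45.2%) | 0.220 (34.3%) | 0.160 (20.4%) |

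At the small end, a 2-point excess with a benefit of 2 points on the 0–20 scale gives 0.02 × 2 = 0.04 points. With an assumed SD of 4, that is 0.04/4 = 0.01 SD, which is trivial. If g is negative, the same formula inflates the contrast.

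**The case against.** **The imbalance is not hidden.** A reader might infer that it cannot be seen at all. That is not so: Listing 16.2.4.3 carries ATC class, preferred term, dates and dose under the treatment received, and SAP 13.2 sorts all listings by treatment. What is lost is the by-arm count and any analysis of its effect. With about 300 subjects, recovering the count means tallying a listing by hand.

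**Listing the deviations is not a departure.** Protocol 13.4.1.2 itself asks only for a by-subject listing, and SAP 6.2 follows it.

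**The SAP does not decide to keep these scores.** It says nothing about them. Confounding is also the wrong word: analgesic use after randomisation is an intercurrent event that the plan leaves unaddressed, and the estimand is worded in terms of randomised treatment without mentioning added analgesics.

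**Some cases are caught elsewhere.** Protocol violation is a ground for removal (protocol 8.2.3), treatment of an adverse event that deviates from the protocol should lead to withdrawal (11.2.4), and rule (i) excludes scores once the patch has been off for more than 24 hours. Corticosteroid use is an optional subgroup in SAP 5.1.8. Removal for violation is discretionary, so the gap is narrower but remains.

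**Frequency and direction are not documented.** Subjects have permitted acetaminophen as an outlet, and its use is compared by arm (Table 14.2.8.1). This stands, and it limits what can be said about size.

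**Conclusion.** Two things hold on the text alone. The protocol's concomitant medication summary has been reduced to a listing while section 9 declares no change. And no rule or named intercurrent event covers WOMAC scores obtained on prohibited analgesics, so they enter the primary MMRM by omission.

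Any effect on the result is conditional. It requires prohibited use to differ between arms or to help one arm more than the other. Dilution of the contrast is the more plausible direction, because subjects without relief have the stronger reason to seek other analgesics, but the documents do not establish it. The illustrative shift runs from 0.01 to 0.16 SD and rests wholly on the assumed imbalance and benefit (and, at the small end, an assumed SD); the comparison with 0.32 also rests on a value not legible in the current text. The point warrants a change because the remedy is cheap and the protocol already requires half of it, not because a material bias has been shown.

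**What to change.** 1. **Restore the table.** Add a concomitant medication table for the Safety population, by arm, with number and percentage, and separate rows for prohibited analgesics used in the double-blind phase. Protocol 13.4.1.3 places this summary among analyses for all analysis populations, so record any restriction to one population. Correct SAP section 9.
2. **Name the intercurrent event.** In SAP 7.1 and 7.1.1, list use of a prohibited analgesic, with the qualifying medications taken from protocol 9.10.2. Add one sensitivity analysis that sets WOMAC scores obtained during such use to missing and applies the 7.1.1 imputation, stating which method. Method 1 is the one already tied to rescue.
3. **Identify affected scores at blinded review before lock, from recorded dates.** The conventions in SAP 5.1.7 move an unknown end day to month-end and an unknown end month to 31 December, and treat a medication with both dates missing as concomitant. Used here, they would flag scores not taken on the drug.
4. **Reconcile the rescue rule.** SAP 7.1 rule (ii) and the YES in the 7.1.1 summary table need to agree, so that rescue and prohibited analgesics are handled consistently. Declare the resulting rule in section 9 if it differs from the protocol.

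Cost: SAP wording, one table and one model run on data already collected on the eCRF. A few scores become missing in that sensitivity analysis.

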6.7. Previous OA treatment modalities

The frequency and percentage of subjects with previous OA related treatment as captured on the concomitant medication eCRF page will be summarized by ATC classification level 4 and preferred term. Also, a summary of previous NSAID treatments will be summarized by ATC classification level 4 and preferred term.

6.8. Exposure and Compliance

The frequency and percentage of the number of patches applied and removed, the number of patches removed early along with reasons for early removal will be tabulated by treatment group and overall for the ITT population.

Within the same table, a summary of the mean duration of exposure will also be calculated. This descriptive summary will include quartiles in addition to the other descriptive statistics normally presented.

A separate summary table will present overall subject compliance with study drug. Compliance is defined as the number of patches given less the number of patches returned divided by the number of days for required applications (e.g. without counting of extra patches given just in case), expressed as a percentage. Number and percentage of subjects who are compliant (defined as using $\geq 80\%$ and $\leq 120\%$ of study medication) and noncompliant (defined as using less than 80% or more than 120% of study medication) at each treatment arm will be presented by weeks and overall. A by-subject listing of all drug exposure information collected will be presented.

7. Efficacy Analysis

All efficacy variables will be summarized and analyzed using the FAS population as the primary population of interest, unless otherwise specified.

7.1. Primary Efficacy Analysis

The estimand in the primary analysis for efficacy for each dose is the difference between treatments groups (each HP-5000 treatment group vs. placebo) in the change from Baseline to Week 4 in WOMAC pain score in all subjects as randomized, under the assumption that all randomized patients remain on their randomized treatment throughout the trial.

AD-ST-33.04 Effective date: 30-Jun-2017

Version 1.0 | Date 21-Oct-2019 | AD-PR-109.01 Effective date: 26-Jun-2017

Page 24 of 124

Statistical Analysis Plan,
 Sponsor Noven Pharmaceuticals, Inc.
 Protocol Number HP-5000-US-05
 [REDACTED]

The comparisons of interest are:

- HP-5000 [REDACTED] versus placebo
- HP-5000 [REDACTED] versus placebo

WOMAC scores obtained 24 hours after removal/detachment of the study medication or WOMAC scores obtained within 24 the subject used rescue medication will be excluded as outliers. Outliers will be defined *a priori* as (i) WOMAC scores obtained more than 24 hours after removal/detachment of double-blind study medication; or (ii) WOMAC scores obtained within 24 hours the subject used rescue medication.

The change from Baseline to Week 4 in the WOMAC pain score will be analyzed using a mixed model repeated measures (MMRM) analysis. The MMRM model will include change from baseline in WOMAC pain score as the repeated dependent variable, with treatment (HP-5000-[REDACTED], HP-5000-[REDACTED], and placebo), visit, treatment-by-visit interaction, and the baseline WOMAC pain score as covariates. The mean difference of change will be compared for each active treatment arm, and overall active against placebo. An unstructured covariance matrix will be assumed. If the unstructured matrix fails to converge, a series of other covariance structures will be tested (AR(1), Toeplitz, and Compound Symmetry). The covariance structure which converges with the lowest Akaike information criterion (AIC) score will be chosen and noted in the resulting table. The Kenward-Roger approximation for denominator degrees of freedom will be implemented, and the restricted maximum likelihood (REML) approach for estimation will be specified in the model code.

Below is example SAS code for conducting the MMRM analysis specified. Note, the macro wrapper used in different covariance structures is not shown below (specified with type option):

[figure not shown]
[figure not shown]
[figure not shown]
```
ods output lsmeans = lsmn1
      lsmestimates = lsmest1
      ConvergenceStatus = MMRMconverge
      Tests3 = MMRMoverall;
proc mixed data=example method=reml;
  class trt avisitn usubjid;
  model chg = trt avisitn trt*avisitn base /alpha=0.05 solution ddfm=kr;
  repeated avisitn/subject=usubjid type=un;
  lsmeans trt*avisitn/cl alpha = 0.05;
  lsmeans trt*avisitn 'Week 1 HP-5000 [REDACTED] vs placebo' 1 0 0 0 0 0 -1 0 0 divisor=1 /cl;
  lsmeans trt*avisitn 'Week 2 HP-5000 [REDACTED] vs placebo' 0 1 0 0 0 0 0 -1 0 divisor=1 /cl;
  lsmeans trt*avisitn 'Week 4 HP- [REDACTED] vs placebo' 0 0 1 0 0 0 0 0 -1 divisor=1 /cl;
  lsmeans trt*avisitn 'Week 1 HP- [REDACTED] vs placebo' 0 0 0 1 0 0 -1 0 0 divisor=1 /cl;
  lsmeans trt*avisitn 'Week 2 HP- [REDACTED] vs placebo' 0 0 0 0 1 0 0 -1 0 divisor=1 /cl;
  lsmeans trt*avisitn 'Week 4 HP- [REDACTED] vs placebo' 0 0 0 0 0 1 0 0 -1 divisor=1 /cl;
  lsmeans trt*avisitn 'Week 1 Overall Active vs placebo' 1 0 0 1 0 0 -2 0 0 divisor=2 /cl;
  lsmeans trt*avisitn 'Week 2 Overall Active vs placebo' 0 1 0 0 1 0 0 -2 0 divisor=2 /cl;
  lsmeans trt*avisitn 'Week 4 Overall Active vs placebo' 0 0 1 0 0 1 0 0 -2 divisor=2 /cl;
run;
```

Statistical Analysis Plan,
Sponsor Noven Pharmaceuticals, Inc.
Protocol Number HP-5000-US-05
PCN Number [REDACTED]

The estimate of the change from baseline to each time point from the model will be presented along with its 95% CI and p-value. The overall p-value of the model will also be presented to test the null hypothesis that there is no change at any timepoint will be presented.

The observed value and change from baseline in the WOMAC pain score will also be summarized descriptively by visit using summary statistics in addition to the above noted model.

Additionally, if the normality assumption is violated by the data, an analysis of covariance (ANCOVA) on rank-transformed data will be used as utility analysis and additional supportive analyses may be performed if necessary. First, the values of the change from baseline variable as well as baseline covariate will be transformed to standardized ranks using fractional ranks and mean method for ties. The ANCOVA will use the same model parameters as the MMRM with all visit effects dropped. [Appendix A](#) contains example code constructed to complete the ANCOVA analyses.

In addition, sensitivity analyses will be performed to test the robustness of the primary result. As described in detail in Section [7.1.1](#), multiple imputation and pattern-mixture models will be implemented on the WOMAC pain score data using the FAS. These analyses are useful in determining if missing-at-random (MAR) and not-missing-at-random (NMAR) missingness patterns are impactful to the model effects and results. These analyses will be performed according to the National Academy of Sciences (2010) guidelines^{[10](#)}.

